2. Over 3-months post-intervention, relative to controls, **BREATHE-PEDS** children will have improvement (a) in asthma control as measured by the *Asthma Control Questionnaire*⁶³⁻⁶⁵ (primary outcome), higher perceived SDM, and (b) on other asthma outcomes (secondary outcomes), including quality of life, school absences, lung functioning, and exacerbation.

Endpoints:

NAME: Asthma Control Questionnaire
TYPE: Primary
TIME FRAME: Focus groups, Baseline and 1-, 2-, and 3-months post intervention

DESCRIPTION: 6-item validated and widely used measure of asthma control
WHO COMPLETES: Child with help from caregiver as needed

NAME: Shared Decision-Making Questionnaire— 9 items
TYPE: Secondary
TIME FRAME: Focus groups, Immediately after the medical visit (i.e., immediate post-intervention)
DESCRIPTION: 9-item validated measure of the decisional process in medical visits from both patients' and physicians' perspectives
WHO COMPLETES: Child AND Caregiver (PATIENT version) and PCP (clinician version)

NAME: Medication Adherence Record Scale-Asthma
TYPE: Secondary
TIME FRAME: Focus groups, Baseline and 1-, 2-, and 3-months post intervention
DESCRIPTION: 10-item validated measure of inhaled corticosteroid adherence (ICS) (dichotomized as high or not). Scores have been shown to predict Self-management as measured by objective electronic monitoring and prescription refill rates.
WHO COMPLETES: Child with help from caregiver as needed

NAME: Conventional and Alternative Management for Asthma
TYPE: Secondary
TIME FRAME: Focus groups, Baseline and 3-months post intervention
DESCRIPTION: 17-item validated measure of erroneous asthma management beliefs (9 items) and ICS beliefs (8 items)
WHO COMPLETES: Child with help from caregiver as needed AND Caregiver

NAME: Pediatric Asthma Quality of Life Questionnaire
TYPE: Secondary
TIME FRAME: Focus groups, Baseline and 1- and 3-months post intervention
DESCRIPTION: 23 questions in 3 domains (symptoms, activity limitation and emotional function). The activity domain contains 3 'patient-specific' questions. Children are asked to think about how they have been during the previous week and to respond to each of the questions on a 7-point scale (7 = not bothered at all - 1 = extremely bothered). The overall PAQLQ score is the mean of all 23 responses and the individual domain scores are the means of the items in those domains
WHO COMPLETES: Child with help from caregiver as needed

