NAME: Pediatric Asthma Caregiver's Quality of Life Questionnaire
TYPE: Secondary
TIME FRAME: Focus groups, Baseline and 1- and 3-months post intervention
DESCRIPTION: 13-item in two domains (activity limitation and emotional function). Parents recall the impact that their child's asthma has had during the previous week and score each question on a 7-point scale.
WHO COMPLETES: caregiver

NAME: Asthma Impairment and Risk Questionnaire (AIRQ) BASELINE
TYPE: Secondary
TIME FRAME: Focus groups, Baseline and 1-, 2-, and 3-months post intervention
DESCRIPTION: 10-item valid and reliable survey that measures both domains of control: symptom impairments and risk for uncontrolled asthma
WHO COMPLETES: Children aged 12 and older

NAME: Asthma Impairment and Risk Questionnaire (AIRQ) FOLLOWUP
TYPE: Secondary
TIME FRAME: 1-, 2-, and 3-months post intervention
DESCRIPTION: 10-item valid and reliable survey that measures both domains of control: symptom impairments and risk for uncontrolled asthma
WHO COMPLETES: Children aged 12 and older

NAME: Brief debriefing survey
TYPE: Secondary
TIME FRAME: Immediately after the medical visit
DESCRIPTION: 10-item (caregiver) and 5-item (PCP) yes/no/short answer survey that asks the participant to recount what happened at the visit
WHO COMPLETES: Three versions Caregiver, Patient AND PCP

NAME: Asthma exacerbation
TYPE: Secondary
TIME FRAME: 1-, 2-, and 3-months post intervention
DESCRIPTION: Oral steroid use 1 year pre- through 1-year post-intervention; report of asthma-related acute care visits, ED visits, and hospitalizations; or Intensification of bronchodilators (to be defined by SMC). All self-reported and/or extracted from provider notes in the electronic health record, confirmed by claims data where available.
WHO COMPLETES: Child and Caregiver

NAME: Asthma Responsibility Questionnaire

Miscellaneous:

TYPE: Secondary
TIME FRAME: Focus groups, Baseline and 1- and 3-months post intervention
DESCRIPTION: 10-item validated measure assessing who is responsible for various asthma care tasks
WHO COMPLETES: Child and Caregiver

NAME: Newest Vital Sign
TYPE: Other
TIME FRAME: Focus groups, Baseline
DESCRIPTION: 6-item validated and widely used measures of health literacy
WHO COMPLETES: Caregiver

NAME: Short Assessment of Health Literacy-Spanish and English
TYPE: Other
TIME FRAME: Focus groups, Baseline
DESCRIPTION: Validated measures of health literacy
WHO COMPLETES: Caregiver

NAME: Asthma Prevention Index
TYPE: Other

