4 STUDY DESIGN

4.1 OVERALL DESIGN

STUDY DESCRIPTION.

Our overall goal is to develop and test **BREATHE-PEDS (BRief intervention to Evaluate Asthma THErapy-Pediatrics)**, a shared decision-making intervention, among low-income urban minority adolescents with uncontrolled asthma.

AIMS. 1) develop **BREATHE-PEDS** in a pediatric population (dyads of caregivers and their 10- to 14-year-old early adolescents with uncontrolled asthma) receiving asthma care in FQHCs; 2) evaluate the feasibility and acceptability of intervention procedures; and 3) assess intervention effects on asthma outcomes (monthly x 3 months post-intervention).

HYPOTHESES.

1. The intervention will be feasible and acceptable as evidenced by: high rates of dyad recruitment and retention; PCP fidelity to the intervention protocol; and PCP and caregiver-child dyad satisfaction.
2. Over 3-months post-intervention, relative to controls, **BREATHE-PEDS** children will have improvement (a) in asthma control as measured by the *Asthma Control Questionnaire*⁶³⁻⁶⁵ (primary outcome), higher perceived SDM, and (b) on other asthma outcomes (secondary outcomes), including quality of life, school absences, lung functioning, and exacerbation.

STUDY PHASE. Phase 1 development and testing a behavioral intervention

STUDY DESIGN. This is a group-randomized clinical trial.

STUDY PROCEDURES.

Aim 1: Focus Groups.

Focus groups. Prior to recruiting for the trial, we will hold focus groups with caregivers (n =20); early adolescents (n =20) and dyads (n =10) (N=60), separately .

Aims 2 & 3: Group-randomized trial. This is a trial of a behavioral/educational intervention comparing the active condition **BREATHE-PEDS (BRief intervention to Evaluate Asthma THerapy-Peds)** to a dose-matched attention control condition (see below for detailed description of conditions). Active and control interventions are delivered once in 9-minutes by the participants' PCP during a single office visit. In each condition there are matched data collection points after baseline: 1-month 2-month, 3-month post-intervention. Considering the potential for visit disruptions due to Covid-19, we offer an alternative plan for the delivery of the intervention at a single telehealth visit (baseline) by phone or HIPAA-compliant videoconferencing platform.

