Control PCPs will use study the web-based app to access the healthy lifestyle scripts and patient participant's ACQ score but will not have access to CAM-A results or **BREATHE-PEDS** scripts. While control participants will receive important nutrition and lifestyle information, the control intervention is not designed to be specific enough to change strategies related to ICS adherence. Further, the control group offers a similar format as BREATHE-PEDS, namely PCP-led discussions in which PCPs use tablets to review ACQ scores and initiate a tailored discussion.

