9 STATISTICAL CONSIDERATIONS

9.1 STATISTICAL HYPOTHESES

Specific Aims:

1. To develop **BREATHE-Peds** in a pediatric population (dyads of caregivers and their 10- to 14-year-old early adolescents with uncontrolled asthma) receiving asthma care in FQHCs;
2. To evaluate the feasibility and acceptability of intervention procedures; and
3. To assess intervention effects on asthma outcomes (monthly x 3 months post-intervention).

Hypotheses:

1. The intervention will be feasible and acceptable as evidenced by: high rates of dyad recruitment and retention; PCP fidelity to the intervention protocol; and PCP and caregiver-child dyad satisfaction.
2. Over 3-months post-intervention, relative to controls, **BREATHE-Peds** children will have improvement (a) in asthma control as measured by the Asthma Control Questionnaire (primary outcome), higher perceived SDM, and (b) on other asthma outcomes (secondary outcomes), including quality of life, school absences, lung functioning, and exacerbation.

MEASURES / ENDPOINTS.

Primary Outcomes: asthma control as measured by improvements in Asthma Control Questionnaire (ACQ) score.

Secondary outcomes: (a) shared-decision-making as measured by scores the Shared Decision-making Questionnaire – 9 items, (b) Self-management as measured by the Medication Adherence Report Scale – Asthma (MARS-A), (c) asthma and ICS beliefs as measured by the Conventional and Alternative Management for Asthma, (d) asthma quality of life as measured by the Pediatric Asthma Quality of Life Questionnaire (PAQLQ) and Pediatric Asthma Caregiver's Quality of Life Questionnaire; and significantly lower rates of (e) asthma exacerbations, (f) symptoms days, (g) nights woken, (h) activity limitations, (i) shortness of breath, (j) wheeze, and (k) rescue medicine use. We will also track Asthma Impairment and Risk questionnaire and Asthma Responsibility Questionnaire scores over time.

Other measures: (1) demographics (age, sex); (2) health literacy as measured by the Newest Vital Sign and the Short Assessment of Health Literacy-English and Spanish; (3) asthma history and (4) lung function as measured by spirometry (COVID permitting).

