9.2 SAMPLE SIZE DETERMINATION

Power & Sample Size. With a sample size of 10 patients/PCP and 4 PCPs in each intervention arm (total $n=10*4*2=80$), and 20% attrition, we calculated the power to test the effect of intervention on outcomes. Power calculations were based on: (1) 4 repeated observations over the 3-month follow-up with a correlation of $p=0.8$ between repeated measures; (2) intra-cluster correlation among PCPs=0.2 to account for clustering of patients from the same PCP; and (3) LMMs to estimate pre- and post-intervention differences. We estimated an 80% power to detect a small effect size ($d=0.15$). For ACQ, this is equivalent to detect a post-intervention difference of 0.15 (assuming $SD=0.9$).

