$y_{ijt} = \beta_0 + \beta_1 * \text{Group} + \beta_2 * t + \beta_3 * \text{INT} + \beta_4 * X_{ij} + \mu_i + \mu_{ij} + \varepsilon_{ijt}$, where group, t , and INT are design variables. Group is an indicator for intervention arm and INT is an indicator for pre- or post-intervention. X_{ij} is a vector of possible PCP- and patient-level covariates. The random term $\mu_i \sim \text{N}(0, \sigma_1^2)$ is a PCP-specific random effect and $\mu_{ij} \sim \text{N}(0, \sigma_2^2)$ is a patient-specific random effect; $\varepsilon_{ijt} \sim \text{N}(0, \sigma_\varepsilon^2)$ is the model random error. To examine the effect of intervention on the outcome, we will conduct hypothesis test of $H_0: \beta_3 = 0$. We will explore differential intervention effect by sex.

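### The test named as the intervention effect (H0: β3 = 0) is on a pre/post indicator shared by both arms, so it does not compare BREATHE-PEDS with control

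*Combined protocol and SAP*

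**What the plan says.** Section 9.4.2, under Aim 3, and the statistical analyses part of Section 4.1 give the same model:

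y_ijt = β0 + β1·Group + β2·t + β3·INT + β4·X_ij + PCP random intercept + patient random intercept + error.

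The design variables are defined thus: "Group is an indicator for intervention arm and INT is an indicator for pre- or post-intervention". X_ij holds PCP- and patient-level covariates and has no time index. The inferential step is: "To examine the effect of intervention on the outcome, we will conduct hypothesis test of" H0: β3 = 0, two-sided at 0.05.

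Four other places bear on what β3 means:

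- Section 4.1 treats both conditions as interventions: "Active and control interventions are delivered once in 9-minutes by the" child's own PCP. It then schedules post-intervention visits at 1, 2 and 3 months in each condition.
- Hypothesis 2 in Section 9.1 is comparative: "Over 3-months post-intervention, relative to controls".
- Section 9.2 bases the power calculation on "3) LMMs to estimate pre- and post-intervention differences" and reports 80% power for d = 0.15, which it equates with 0.15 ACQ points at SD 0.9.
- In the Section 1.1 endpoint list, the SDM-Q-9 entry reads "TIME FRAME: Focus groups, Immediately after the medical visit (i.e., immediate post-intervention"; the table in Section 8 likewise shows no baseline value for it.

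**The concern.** INT is defined by time alone, and both arms pass through the same pre/post boundary. The model has no Group × INT or Group × t term, and none can sit inside X_ij because X_ij does not vary over time. So β3 is the step after the visit, beyond the common slope, averaged over the two arms. β1 does not fill the gap: it is a constant arm difference that includes baseline. For ACQ, no coefficient isolates change relative to controls.

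A shared improvement is plausible. Every child screens positive for uncontrolled asthma and sees their PCP, and Section 6.1.1 describes the control format as similar to the active one, "namely PCP-led discussions in which PCPs use tablets to review ACQ scores and initiate a tailored discussion". If that improvement comes soon after the visit, the stated test credits it to the intervention. In the other direction, an effect confined to the active arm is halved or lost.

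For SDM-Q-9, INT equals 1 at every observation, so β3 cannot be estimated at all. Exacerbation is less clear-cut. Its time frame is months 1–3, but its description includes "Oral steroid use 1 year pre- through 1-year post-intervention", so only components with no pre-visit value share the problem.

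**Working it through.** **Inputs (Section 9.2).** 8 PCPs × 10 dyads = 80; 20% attrition leaves 64, or 32 per arm and 8 per PCP. SD 0.9, correlation between repeated measures 0.8, PCP ICC 0.2, two-sided 0.05. I take the four observations as baseline plus months 1, 2 and 3, with t = 0, 1, 2, 3 and INT = 0, 1, 1, 1. Power and rejection rates use the normal approximation unless stated.

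**The stated 80%.** Within-patient error variance = 0.81 × (1 − 0.8) = 0.162. Variance of one child's mean follow-up minus baseline = 0.162 × (1 + 1/3) = 0.216.

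- Pooled pre/post change of 0.15 points: SE = √(0.216/64) = 0.058, power 73%. With all 80 dyads, SE = 0.052, power 82%.
- Difference in change between arms of 0.15 points: SE = √(2 × 0.216/32) = 0.116, power 25%. With all 80, SE = 0.104, power 30%.

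The stated figure is not reproduced exactly. It lies near the pooled pre/post contrast and far from the between-arm one.

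**Standard error of β3 as written.** Within a child, the centred sums of squares are 5 for t and 0.75 for INT, with cross-product 1.5. INT adjusted for t has 0.75 − 1.5²/5 = 0.30. Hence SE(β3) = √(0.162/(64 × 0.30)) = 0.092.

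**What each test picks up.** Expected β3 is the projection of the true change on (1, t, INT), averaged over arms. Sizes and shapes of change are assumed.

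| True improvement in ACQ | Expected β3 | β3 test rejects | Group × INT rejects |
|---|---|---|---|
| Both arms, step 0.1 | 0.10 | 19% | 5% |
| Both arms, step 0.2 | 0.20 | 59% | 5% |
| Both arms, step 0.3 | 0.30 | 90% | 5% |
| Both arms, step 0.5 | 0.50 | 100% | 5% |
| Both arms, 0.15 at month 1, 0.3 from month 2 | 0.10 | 19% | 5% |
| Both arms, linear | 0 | 5% | 5% |
| Active only, step 0.30 | 0.15 | 37% | 73% |
| Active only, linear to 0.30 at month 3 | 0 | 5% | 41% |
| Active better by 0.25, control worse by 0.25 | 0 | 5% | 99% |

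β1 is no substitute: its SE is 0.34, and a true post-visit arm difference of 0.5 is detected only 20% of the time.

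**Power for the between-arm contrast.** d = 0.15 at SD 0.9 is 0.15 × 0.9 = 0.135 points, not 0.15, so both are shown. SE = √(2 × 0.216 × (1 + 7 × ICC)/32) at 64 completers.

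| PCP ICC of change | SE | Power, 0.135 / 0.15 | Same on 6 df |
|---|---|---|---|
| 0 (PCP effect cancels) | 0.116 | 21% / 25% | 17% / 19% |
| 0.2 | 0.180 | 12% / 13% | 10% / 11% |

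With no PCP variation in change, the difference detectable with 80% power is 2.80 × 0.116 = 0.33 points at 64 completers (0.29 at 80).

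**Is adding Group × INT enough?** Only if PCPs do not differ in how much their patients change. Holding total change variance at 0.216 and assigning 5%, 10% or 20% of it to PCPs (assumed shares), a model with only the stated random intercepts has type I error of 9.8%, 15.5% and 24.7% in 10,000 simulated trials. A PCP-level t-test on 6 df stays between 4.6% and 4.9%.

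**The case against.** The best defence is that INT was meant to equal 1 only at post-visit observations in the BREATHE-PEDS arm. Group, time and INT would then form a difference-in-differences layout, and β3 would be the arm comparison, in line with Hypothesis 2. The plan does not say this, and Section 4.1 applies the term post-intervention to each condition. Nor would that coding work with a single slope for t. Having no main effect for post, the model would put 4/7 (57%) of a shared step onto β3: a shared 0.3 step with no arm difference gives β3 = 0.17 with SE 0.098 and 42% rejection, and a 0.5 step gives 83%. The coding is sound only if t enters by visit.

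The plan also does not say outright that t is linear; the single β2 implies it. Entering t by visit under the written definition makes INT the sum of the follow-up indicators, so β3 cannot be estimated.

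Three points on the other side stand. The false-positive risk depends on shape: it is about 5% if shared improvement is purely linear and 19% if it builds over two months. Section 9.2 gives the 0.2 ICC for patients of the same PCP, not specifically for change, so the 12–13% power is the less favourable case. The documents also mention 85 dyads and 90% providing data; 85 × 0.9 = 76.5 would raise between-arm power at 0.15 points to about 29%. None of these makes β3 the arm comparison.

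The trial is a feasibility study, but ACQ is its named primary outcome, tested formally at 0.05.

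**Conclusion.** The concern holds. As written, the primary test does not test the primary hypothesis. This follows from the model and the definition of INT, and needs no numerical assumption.

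The size of the harm does depend on assumptions. With 64 completers, SD 0.9 and correlation 0.8, a shared immediate step of 0.1 to 0.5 points produces a false claim of effect in 19% to 100% of trials, and an active-only step is estimated at half its size. An active-only linear gain is invisible to the test.

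The stated 80% power does not apply to the comparison with controls. The figure for that is 21–25%, falling to 12–13% if change is clustered by PCP with ICC 0.2. For SDM-Q-9, the named test cannot be run. The model needs correcting under any reading of INT and t that the text allows.

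**What to change.** 1. In Sections 4.1 and 9.4.2, define INT explicitly, add a Group × INT term (or Group by categorical month), and name that term as the primary hypothesis test.
2. Add a PCP-by-INT random effect with small-sample degrees of freedom (about 6 for 8 PCPs), or analyse mean change at PCP level. With four PCPs per arm the extra variance will be poorly estimated, so the PCP-level analysis is the simpler choice.
3. For SDM-Q-9, and any exacerbation component with no pre-visit value, test Group in a model of post-visit data only.
4. In Sections 4.1 and 9.2, restate power for the between-arm contrast, with one consistent effect size (0.135 or 0.15 points). Alternatively, say that the trial will estimate the effect with a confidence interval and is not powered to test it.

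The cost is text edits to the model and test in two places and to the power statement in two places, with no new data or participants. Stated power becomes much less favourable, and the interval widens once PCP-level change is allowed for.

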TIME FRAME: Baseline and 1-, 2-, and 3-months post intervention
DESCRIPTION: 11 item index measuring how many steps and the regularity in which the steps are taken to prevent symptoms from occurring.
WHO COMPLETES: Child and Caregiver

Asthma history (e.g. age at diagnosis); Demographics
TYPE: Other
TIME FRAME Baseline
WHO COMPLETES: Caregiver

Study Population:

Aim 1: Focus groups (pre-trial). We will enroll caregivers (n =20) ; early adolescents (n =20) and dyads (n =10) (N=60) into separate focus groups.

Aims 2 & 3: Group-randomized trial. We will recruit 85 dyads and 8 clinicians to the trial.

Aims 2 & 3: Post-trial interviews. We will do post-trial interviews with a purposive sample of ~6 participating clinicians, ~10 early adolescents, and ~10 caregivers.

Inclusion of Women.

Caregiving participants in focus groups and the group-randomized trial. We anticipate enrolling more female caregivers than men because more women serve in the caregiving role. We therefore estimate that ~75% of our caregiving participants in this trial will be female. We will explore if there is a differential intervention effect by sex.

Provider participants (group-randomized trial). Based on the sex of the clinicians working at these sites, we anticipate that 75% of our 16 clinicians will be female.

Inclusion of Minorities.

Patient participants in focus groups and the group-randomized trial. Asthma prevalence and morbidity is increased in Latino (defined as a person of Cuban, Mexican, Puerto Rican, Cuban, South or Central American, or other Spanish culture or origin, regardless of race) and Black (defined as a person having origins in any of the black racial groups of Africa) youth. They also have more asthma-related emergency department (ED) visits and hospitalizations. To address these health disparities, we have partnered with Urban Health Plan, Inc. (UHP), a federally qualified health center (FQHC) that serves a predominantly Latino and/or Black community. Based on demographic data provided by UHP we anticipate that 95% of the adolescents will be ethnic-racial minorities with 85% Latino and 10% non-Hispanic Black; the racial/ethnic distribution of their caregivers is expected to be similar. Our team has extensive experience working in ethnically diverse populations, particularly in the context of asthma intervention research.

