Aim 2: Post-Trial Interviews. The PI will conduct post-trial semi-structured interviews with a purposive sample of ~6 participating clinicians, ~10 patient participants, and ~10 caregivers to ascertain their satisfaction with, and acceptability of, the active and control interventions. As part of our implementation evaluation, attempts will also be made to interview patient participants and PCPs who withdraw from the study (or PCPs who decline to enroll, if we have any), to better understand what it was that prevented their continued participation.

RANDOMIZATION.

We will randomly assign all eligible clinicians equally into the **BREATHE-PEDS** and the dose-matched attention control condition stratified for provider type (physician vs. nurse practitioner [NP]/physician assistant [PA]) using a computer-generated randomization list in advance of the trial. The first four physicians and first four NPs/PAs in each condition (**BREATHE-PEDS** and control) will then be invited to enroll (N=8). Those not selected (i.e., those remaining on the list) will be placed on "standby" if a replacement is needed. Invited PCPs signing consent will then be trained on the condition to which they were randomized. Each PCP will then enroll ~10 dyads meeting inclusion/exclusion criteria (N =85).

STATISTICAL ANALYSES.

Development and Intervention Feasibility. We will document recruitment, randomization and retention success, as well as process and implementation assessments.

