9.4.2 ANALYSIS OF THE PRIMARY AND SECONDARY ENDPOINT(S)

Analytic Plan.

Aims 1 & 2: Development and Intervention Feasibility. We will document our success in meeting recruitment and randomization goals, as well as process (recruitment outreach and numbers meeting eligibility criteria who accept or decline enrollment) and implementation assessments (retention rates, data completion rates, as well as fidelity, contamination and masking in the clinical trial arm).

Randomization. This is a group-randomized trial in which the primary care providers (PCPs) will be randomized within sites to the active and control conditions. We will utilize a stratified block randomization plan, stratifying by provider type (physician vs. nurse practitioner/physician assistant), to insure equal numbers of PCPs within each PCP type are assigned to each condition. Randomization lists will be computer-generated in advance by our biostatistician. Outcomes will be analyzed at the level of the early adolescent and/or caregiver.

Masking. Participants and data collectors will be masked to study hypotheses and group assignment; the investigators will be blinded to group assignment. PCPs in both intervention conditions will use tablets as part of their respective interventions and have sessions audio-recorded, facilitating masking of participants and data collectors.

Aim 3: Intervention Effects. Intervention effects will be assessed using linear mixed models (LMM) or generalized linear mixed models (GLMM) for continuous and categorical outcomes, respectively. All hypothesis tests will be two-sided at level $\alpha=0.05$. The key outcome will be ACQ score; secondary measures will be examined to inform the future RCT. Separate models will be fitted for different outcome measures. If y_{ijt} is the outcome for patient j of provider i at time t , without loss generality then the following LMM will be used:

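### The only PCP term in the ACQ model is a constant intercept, so clustering by PCP drops out of the tested pre/post contrast and the 5% level depends on PCPs not differing in change

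*Combined protocol and SAP*

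**What the plan says.** Section 9.4.2 randomises PCPs and models y_ijt with fixed effects for Group, t, INT and covariates X_ij, plus three random parts: mu_i, mu_ij and a residual with a single variance. The first "is a PCP-specific random effect and" the second is specific to the patient. Neither carries a time index. Section 4.1 gives the same model. "INT is an indicator for pre- or post-intervention", and the intervention effect is tested as beta_3 = 0, two-sided at 0.05.

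Section 9.2 starts "With a sample size of 10 patients/PCP and 4 PCPs in each intervention arm", allows 20% attrition, and assumes a correlation of 0.8 between repeated measures and an "intra-cluster correlation among PCPs=0.2 to account for clustering of patients from the same PCP".

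Neither section states a PCP-by-period term, a cluster-robust variance, or degrees of freedom based on the number of PCPs.

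**The concern.** In a group-randomised trial with baseline and follow-up on the same patients, the error that matters for the arm comparison is how much clusters differ in their mean change. A PCP intercept describes how much PCPs differ in level, and that difference is removed when pre is subtracted from post. The model therefore looks as if it allows for clustering, while the tested standard error treats patients as independent with respect to change.

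If PCPs do differ in change, the ACQ p-value and confidence interval for Hypothesis 2 are too favourable, and differences between a few clinicians can pass for an intervention effect in any arm comparison. No section ties progression to this p-value. What is at stake is the stated 5% test and the precision that the pilot reports to inform the later RCT.

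The point is limited to continuous outcomes measured before and after. Section 9.4.2 assigns LMMs and "generalized linear mixed models (GLMM) for continuous and categorical outcomes, respectively", and exact cancellation does not carry over to the GLMM outcomes, such as the adherence scale that the synopsis dichotomises. Nor does it apply to the SDM questionnaire, which is measured once.

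**Working it through.** **Inputs.** From section 9.2: 4 PCPs per arm, 10 patients each, 20% attrition (so 8 per PCP, 32 per arm, 64 in all), ICC 0.2, correlation 0.8, SD 0.9. From the synopsis: one pre and three post ACQ measures. With total variance 1, this gives PCP 0.2, patient 0.6, residual 0.2.

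**The plan's own figure.** Section 9.2 claims 80% power at d = 0.15. Power = Phi(d/SE - 1.96).
- Between-arm difference in change: SE = sqrt(2 x 0.2 x (1 + 1/3)/32) = 0.1291; 0.15/0.1291 - 1.96 = -0.80; power 21%.
- Pooled pre/post change, ignoring t: SE = sqrt(0.2 x (1 + 1/3)/64) = 0.0645; power 64%.
- Post-only comparison, where the ICC does enter: SE 0.376; power 6%.

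None of these gives 80%, so the power statement does not show how the ICC was used.

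**Step 1: does the ICC reach the tested standard error?** Three readings of the test:
- beta_3 as written, INT = pre/post in both arms. With t = 0, 1, 2, 3 in the model, the within-patient sum of squares for INT after adjusting for t is 0.75 - 1.5^2/5 = 0.30. SE = sqrt(0.2/(64 x 0.30)) = 0.1021.
- INT read as Group x post: 0.75 x 32 - (1.5 x 32)^2/(5 x 64) = 16.8. SE = sqrt(0.2/16.8) = 0.1091.
- A Group x INT term added: SE = 0.1291, as above.

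The PCP variance appears in none of these. A full GLS calculation, with the residual held at 0.2, gives the same three values at ICC 0, 0.05, 0.1, 0.2, 0.3 and 0.5. With 10 enrolled per PCP and 20% random monotone dropout, moving the ICC from 0 to 0.5 changes the Group x INT SE by at most 0.0007 (0.1232 v 0.1225) and that of beta_3 by at most 0.0002.

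**Step 2: what if PCPs differ in change?** Let r be the correlation between a PCP's pre and post effects. This is an assumption, because the documents give no value. The PCP-level variance of change is 2 x 0.2 x (1 - r) = 0.4(1 - r), and the SD in ACQ points is 0.9 x sqrt(0.4(1 - r)). The true variance is the model variance plus:
- beta_3: 0.4(1 - r)/8
- Group x INT: 2 x 0.4(1 - r)/4

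Example, Group x INT at r = 0.95: sqrt(0.01667 + 0.01) = 0.163. Type I error = 2(1 - Phi(1.96 x 0.1291/0.163)) = 12.1%.

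| r | SD of PCP change (ACQ points) | beta_3 as written: closed form (simulated) | Group x post: closed form | Group x INT: closed form (simulated) |
|---|---|---|---|---|
| 1.0 | 0 | 5.0% (5.0%) | 5.0% | 5.0% (5.1%) |
| 0.98 | 0.08 | 6.1% (6.3%) | 7.3% | 7.8% (7.6%) |
| 0.95 | 0.13 | 7.8% (7.7%) | 10.9% | 12.1% (11.6%) |
| 0.9 | 0.18 | 10.7% (10.1%) | 16.5% | 18.6% (17.8%) |
| 0.8 | 0.25 | 16.2% (14.1%) | 25.7% | 28.8% (27.4%) |

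The simulations used 20,000 trials per cell with the residual variance estimated. At larger PCP variation they fall a little below the closed form, because the fitted residual absorbs part of it. For Group x post, separate simulations gave 10.1%, 14.8% and 23.8% at r = 0.95, 0.9 and 0.8. With 9 completers per PCP (the 90% expected in section 9.4.1), the closed form for Group x INT at r = 0.8 is 30.8%.

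Section 9.2 does not say whether its ICC refers to level or to change. If 0.2 applied to change, the design effect would be 1 + 7 x 0.2 = 2.4 and type I error 2(1 - Phi(1.96/sqrt(2.4))), about 21%.

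**Step 3: an analysis at PCP level.** A t-test on the 8 PCP mean changes (6 df) holds 4.9-5.1% across the same range of r, and 5.0-5.1% with unequal cluster sizes from dropout.

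**Number of PCPs.** Most sections state 8, but the synopsis says "we anticipate that 75% of our 16 clinicians will be female" and section 4.1 invites "The first four physicians and first four NPs/PAs in each condition", which adds to 16 although that sentence ends with N = 8. If 64 completers were spread over 16 PCPs (4 each, a constructed case), the closed form across the same r is 5.0, 5.6, 6.4, 7.8 and 10.7% for beta_3, and 5.0, 6.4, 8.6, 12.1 and 18.6% for Group x INT.

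**The case against.** The algebra is not in dispute. The best counter-arguments concern size and priority.

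- **The largest figures belong to a term the plan does not contain.** True: as written, the simulated range is 5-14%. Without a Group x INT term, beta_3 is not an arm contrast at all, and a change common to both arms can produce rejection. That is a separate and prior defect. Once it is repaired, the Group x INT column is the one that applies.
- **Equal change across PCPs is necessary for 5% but not sufficient.** True: patient-level variation in change alone gave 6.9% in one scenario. This adds a second reason for doubt and does not rescue the model.
- **Large PCP differences around one scripted nine-minute contact are unlikely.** Sections 6.1.1 and 6.2.1 do push PCPs together through scripts, fidelity review and, in the active arm, a proficiency test. At r = 0.8 the PCP-level SD of 0.25 points exceeds the planned difference of 0.15, so the top of the range should not be read as an estimate. But equal asthma care between arms does not make individual PCPs alike. Section 2.3.1 leaves medical management open, and section 6.2.1 retains PCPs who omit elements or who teach asthma self-care in the control arm.
- **This is a feasibility trial.** That limits the consequence, but a 5% test and an interval are still specified.

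**Conclusion.** The concern holds. For ACQ and other continuous pre/post outcomes, the planned ICC of 0.2 does not enter the standard error of the tested contrast: exactly so with complete data, and almost exactly with 20% dropout. This rests only on the written model. PCP clustering leaves the 5% level intact only if PCPs do not differ in their patients' mean change, and nothing in the analysis plan allows for the alternative.

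The size of the inflation rests on an assumed r. With 8 PCPs, simulated type I error runs from 5% to about 14% for beta_3 as written, to about 24% if INT means Group x post, and to about 27% for Group x INT, as r falls from 1 to 0.8. A PCP-level SD of change of 0.13 ACQ points is enough to more than double the nominal level for Group x INT. The plan should be changed, but the consequence is bounded by the feasibility purpose.

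**What to change.** In sections 9.4.2 and 4.1, together with a Group x INT term:

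- Add a PCP x INT random effect. Test Group x INT with small-sample degrees of freedom equal to the number of PCPs minus 2 (6 for 8 PCPs, 14 for 16), reduced further if site or provider type is also modelled for change. Keep these degrees of freedom even if the new variance is estimated as zero.
- Alternatively, make a t-test on PCP mean changes, with the same degrees of freedom, the primary inference.
- State the final number of PCPs.
- Use PCP-based degrees of freedom for outcomes measured once, such as the SDM questionnaire.

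This needs analysis wording and one variance component, and no new data. The cost is precision. For Group x INT with 8 PCPs, the effect detectable with 80% power is 0.36 SD under the present error term (2.80 x 0.1291). Under the corrected test it is 0.435 SD if PCPs do not differ in change, and 0.48, 0.55, 0.645 and 0.80 SD at r = 0.98, 0.95, 0.9 and 0.8. With 16 PCPs it is 0.39 SD, and 0.41, 0.44, 0.49 and 0.58 SD. The 80% power claim at d = 0.15 in section 9.2 should be revised to match.
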